All study-specific samples tested to determine HIV status must be whole blood, serum, or plasma. Testing methods and algorithms must be approved for each site by the IMPAACT Laboratory Center. Testing methods should be FDA-approved, if available.

Note: Test results may be obtained from medical records or from testing performed during the study screening period, as follows:

- For results obtained from medical records, adequate source documentation, including the date of specimen collection, date of testing or date of test result, name of test/assay performed, and test result, must be available in study records prior to study entry. Requirements related to laboratory operations (e.g., Good Clinical Laboratory Practices [GCLP], or Virology Quality Assurance [VQA]) and related to regulatory authority approvals (e.g., FDA) do not apply to results obtained from medical records.
- If adequate source documentation is not available, Sample #1 and/or Sample #2 must be collected during the study screening period and tested in the study site's designated testing laboratory. If both samples are tested using antibody tests, at least one of the samples must be tested in a laboratory that operates according to GCLP guidelines and participates in an appropriate external quality assurance program. If nucleic acid testing is used, at least one test must be performed in the study site's VQA-certified laboratory.

4.1.4 At screening, aware of their HIV infection status, as determined by the site investigator.

4.1.5 At screening, has been prescribed ART for a minimum of 24 weeks prior to screening as determined by the site investigator based on participant/parent or guardian report and/or medical records.

4.1.6 At screening, meets at least one of the following indicators of moderate to severe mental health symptomology:

- Patient Health Questionnaire-9 (PHQ-9) score  $\geq 10$
- General Anxiety Disorder-7 (GAD-7) score  $\geq 10$
- UCLA Post-Traumatic Stress Disorder-Reaction Index (UCLA PTSD-RI) score  $\geq 35$

Note: Severe distress or suicidal ideation is not exclusionary.

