## 6.3 Youth Randomized Trial of TI-CBT

### 6.3.1 Youth Randomized Trial: Screening Visit

Screening procedures may be initiated after written informed consent/assent is obtained. Screening procedures for the Randomized Trial are targeted to be performed within a target window of up to 30 days prior to the enrollment and an allowable window of up to 60 days prior to enrollment. Multiple visits may be conducted to complete all required screening procedures if necessary. For youth who do not meet the eligibility criteria, screening may be discontinued once ineligibility is determined.

Youth Screening Visit Procedures for Randomized Trial (up to 60 days prior to enrollment)		
Administrative and Regulatory		
 
• Obtain written informed consent with written assent as applicable per inclusion criterion 4.1.2 and documentation of youth permission for caregiver participation in the study
 
• Assign participant identification number (PID)
 
• Obtain screening number from study-specific screening log in SES
 
• Assess eligibility
 

Clinical		
 
• Review medical records to assess study requirements related to HIV infection per inclusion criterion 4.1.3 and ARV history per inclusion criterion 4.1.5, and collect limited demographic screening data
 

Behavioral and Counseling		
 
• Administer electronic questionnaires - pen and paper may be substituted per Section 10.1: 
 
Eligibility and baseline measures: 
 
○ PHQ-9
 
○ GAD-7
 
○ UCLA PTSD-RI
 
 
 
Baseline measures only: 
 
○ Demographics
 
○ Self-reported ART Adherence
 
 
 
 
 

Laboratory	Blood	
 
• Collect blood only if needed per inclusion criterion 4.1.3 for: 
 
○ Confirmatory HIV testing
 
 
 

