### **9.5.1 Primary Outcome Measures**

The primary analysis for IMPAACT 2016 will focus on outcome measures at six months, because the protocol team believes that in order to see the full effect of the intervention, participants must have time post-intervention to incorporate and use the skills they learned from TI-CBT. It is expected that the three mental health measures (PHQ-9, GAD-7, UCLA PTSD-RI) will be correlated; they will therefore be analyzed as a composite measure for the primary analysis, which will be constructed by standardizing participants' scores on the three mental health measures and summing them. These scores will be standardized to all be on the same scale, with mean 0 and standard deviation 1 (173). The internal consistency of this composite will be checked by examining Cronbach's alpha for the three standardized mental-health measure scores to see if they form a coherent measure.

The primary analysis for comparisons of the composite score between arms will be a cluster-level analysis. For cluster randomized trials, one valid method for analyzing intervention effects is to compute the mean for each group and then do a two-sample t-test on the site-specific measures (174). Hoover (175) recommends using the Satterthwaite t-test for unequal variances for individually randomized group trials, to take into account the possibility of intervention and control arms having different variances. The same procedure will be done to analyze each individual mental health measure.

Supplementary analyses using individual data will also be conducted to incorporate both individual and group characteristics as covariates and allow a multivariate outcome. Potential covariates include gender, caregiver participation, route of infection, and reported contamination between groups. The three primary outcome measures will be standardized as above and used as a multivariate outcome measure in a mixed model, with individual group as a random effect and individual participants nested within groups (to account for group effects). If there are significant

differences between groups, site and group characteristics (such as number of visits) will be examined for incorporation into the mixed models.

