3.1 Primary Outcome Measures

The primary outcome measures used to address the study's primary objective are the following measures of mental health at 6 months after entry:

1. Patient Health Questionnaire-9 score (PHQ-9, measure of depression);
2. General Anxiety Disorder-7 score (GAD-7, measure of anxiety);
3. UCLA Post-Traumatic Stress Disorder-Reaction Index (UCLA PTSD-RI, measure of PTSD);
4. Composite mental health measure (PHQ-9, GAD-7, and UCLA PTSD-RI scores will be standardized and then summed).

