4.2 Analysis Approaches

4.2.1 Analysis of the Primary Objective

The primary efficacy analysis will compare all primary outcome measures between randomized arms using the ITT analysis population. The primary outcome measures will be analyzed using a two-sided type I error rate of 0.05 and associated 95% confidence intervals in comparing differences between randomized arms. There will be no statistical adjustment for multiple comparisons. Only complete cases, i.e., youth with data for a specified measure, will be analyzed.

It is expected that the three mental health measures (PHQ-9, GAD-7, UCLA PTSD-RI) will be correlated; they will therefore be analyzed jointly using a composite measure. The three measures will first be standardized to the same scale, with mean 0 and standard deviation 1. Standardization will be done for each measure by subtracting the baseline (Pre-Entry) overall variable mean from each observation and dividing by the baseline pooled sample standard deviation. Resulting standardized scores thus represent the number of standard deviations from the baseline mean. Internal consistency of the mental health composite will be checked by examining Cronbach's alpha for the three standardized mental health measures to see if they form a coherent measure, indicated by an alpha greater than or equal to 0.70. If coherent, the composite mental health score will be created by summing the standardized scores within-youth.

The primary analysis comparing the composite mental health measure between arms will be a group-level analysis. One valid method for analyzing intervention effects within cluster randomized trials is to compute the mean for each cluster and then perform a t-test on the cluster-specific summaries. Here, a paired t-test will be performed for the difference in means between arms, with pairs defined by each distinct combination of site and wave. The same procedure will be used to analyze each mental health measure separately.

Supplementary Analyses

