mental health measure compromised only of the GAD-7 and PHQ-9, regardless of Cronbach's alpha.

To investigate sources and impacts of bias, primary analyses will also be repeated (1) within the MITT analysis population, described below; and (2) using imputed data, described in Section 4.2.3, rather than a complete case approach.

ITT analyses are the only analyses protected by randomization, i.e., both measured and unmeasured confounders will be balanced between randomized arms thus providing an unbiased treatment effect, and represent the analysis standard for RCTs. However, in the presence of multiple eligibility or enrollment errors, the ITT analysis population may not reflect the target analysis population of IMPAACT 2016. For example, mental health symptoms may be less severe than expected if youth were enrolled with mental health scores less than the eligibility thresholds (i.e., PHQ-9 \geq 10, GAD-7 \geq 10, UCLA PTSD-RI \geq 35). To assess the degree to which external generalizability of trial findings may be impacted by these protocol deviations, analysis will be repeated among the MITT analysis population which excludes them, and effects estimated among the ITT and MITT analysis populations will be compared. Hypothesized mechanisms for any observed differences between effects will be discussed in publications and presentations of trial results.

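### The SAP makes the three-scale composite primary outcome conditional on Cronbach's alpha of at least 0.70, names no visit for alpha and gives no rule for failure, in conflict with SAP 3.1 and protocol 9.5.1

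*SAP*

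**What the plan says.** SAP 4.2.1 standardizes the three scales and examines Cronbach's alpha, with coherence "indicated by an alpha greater than or equal to 0.70". The next sentence reads: "If coherent, the composite mental health score will be created by summing the standardized scores within-youth". No visit is named for alpha, and no sentence covers alpha below the threshold.

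Other places treat the composite differently:

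- SAP 3.1 lists it as the fourth primary outcome with no condition: "Composite mental health measure (PHQ-9, GAD-7, and UCLA PTSD-RI scores will be standardized and then summed".
- Protocol 9.5.1 makes the composite the primary analysis. It examines alpha "for the three standardized mental-health measure scores to see if they form a coherent measure", with no threshold and no consequence.
- Protocol 9.3.1 names the composite as the primary efficacy outcome in the sample size section.
- Under Supplementary Analyses, SAP 4.2.1 adds a two-scale composite if more than 10% of UCLA PTSD-RI assessments are unscorable. That is a "mental health measure compromised only of the GAD-7 and PHQ-9, regardless of" Cronbach's alpha.

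The three single scales are also primary outcomes. Each is tested by the same procedure, without multiplicity adjustment.

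Two further provisions matter. Protocol 4.1.6 admits a youth who "meets at least one of the following indicators of moderate to severe mental health symptomology", that is, any one of three cutoffs. The standardization rule in SAP 4.2.1 says: "Standardization will be done for each measure by subtracting the baseline (Pre-Entry) overall variable mean from each observation". SAP 4.1.2 likewise defines baseline as the Pre-Entry visit. Protocol 6.3.1 gives the three scales at Screening, under the label "Eligibility and baseline measures"; protocol 6.3.2 and Appendix II-A do not schedule them at Pre-Entry.

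**The concern.** Whether the lead outcome exists would be settled by a correlation in the trial's own data, under a condition that the protocol does not contain. The exemption for the two-scale composite confirms that the three-scale composite really is conditional, so a supplementary composite is better protected than the primary one.

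The condition is not needed for validity. Randomization makes a between-arm comparison of a sum of standardized scores valid at any alpha, and alpha bears only on how that sum is interpreted.

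If the threshold is missed, three tests at 0.05 remain and the plan does not say which leads. Because alpha has no stated visit, the choice of visit could itself decide whether the composite is tested. SAP 4.2.2 applies the same procedure at the immediate post-last-session visit, so it is also open whether alpha would be tested again there.

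**Working it through.** **1. The plan's own figure.** Table 5 gives the detectable difference in SD units. With m groups per arm of size n, SE = sqrt(2 × (1 + (n − 1) × ICC) / (m × n)), using a noncentral t with 2(m − 1) df, 80% power and two-sided 0.05.

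- m = 16, n = 8, ICC 0.05: SE = sqrt(2 × 1.35 / 128) = 0.145; detectable difference 0.421 (Table 5: 0.42).
- m = 12, n = 8, ICC 0.15: SE = sqrt(2 × 2.05 / 96) = 0.207; detectable difference 0.606 (Table 5: 0.61; the text of protocol 9.3.1 says 0.62).

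All 36 cells reproduce, with a largest difference of 0.004. Alpha does not enter, so removing the condition leaves these figures unchanged.

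**2. What the threshold requires.** For three standardized scales with mean correlation r, alpha = 3r / (1 + 2r). Setting alpha = 0.70 gives r = 0.70 / (3 − 1.4) = 0.4375.

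**3. Assumptions for the effect of the eligibility rule.** SAP 4.2.1 expects the scales to correlate but gives no value, so r was varied from 0.5 to 0.8 among screened youth. Protocol 1.3.3 cites 20% and 23% for depression, 22% for post-traumatic stress disorder, and 25-45% for significant distress overall. None of these is stated at the trial's cutoffs, and no anxiety figure is given. Scores are taken as trivariate normal. With 23%, 23% and 22% above the cutoffs, 38-43% of youth are eligible for r of 0.5 to 0.7.

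**4. Alpha after selection.** Simulated youth were kept if any score exceeded its cutoff. For 6 months, with rho the correlation of a score with itself from Screening to 6 months, covariance = rho² × (selected covariance) + (1 − rho²) × (unselected covariance). Results for the 23/23/22% cutoffs:

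| r before selection | alpha before | alpha at Screening | 6 months, rho 0.3 | rho 0.5 | rho 0.7 |
|---|---|---|---|---|---|
| 0.5 | 0.75 | 0.25 | 0.73 | 0.69 | 0.60 |
| 0.6 | 0.82 | 0.41 | 0.80 | 0.77 | 0.71 |
| 0.7 | 0.875 | 0.57 | 0.86 | 0.84 | 0.80 |
| 0.8 | 0.92 | 0.71 | 0.92 | 0.90 | 0.87 |

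Moving the cutoffs over 20-25% gives Screening alpha of 0.38-0.44 at r = 0.6, 0.54-0.59 at r = 0.7 and 0.69-0.73 at r = 0.8.

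Five cutoff settings were tried, with 10% to 30% above a cutoff. Screening alpha was below 0.70 in 17 of 20 scenarios that passed before selection. At 6 months it was below 0.70 in 12 of 60: ten at r = 0.5 with rho of 0.5 or more, and two at r = 0.6 with rho = 0.7.

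**5. Chance that the sample alpha misses 0.70** (n = 173 to 256, that is 192 less 10% up to 256; 23/23/22% cutoffs).

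- At Screening: 100% at r = 0.6, at least 99.8% at r = 0.7, and 34-38% at r = 0.8.
- At 6 months with r = 0.6: at most 0.1%, 1-2% and 42-45% for rho of 0.3, 0.5 and 0.7. At r of 0.7 or more: at most 0.2%.

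**6. What is lost.** Three tests at 0.05 have a familywise error of at most 1 − 0.95³ = 14.3% if independent, and less if positively correlated. If each scale has the same effect d in SD units, the composite has effect 3d / sqrt(3 + 6r) = d × sqrt(3 / (1 + 2r)). That is 1.12d at r = 0.7, 1.26d at r = 0.4375 and 1.46d at r = 0.2. On that assumption, the condition removes the composite where it adds most to power.

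**The case against.** Checking that summed scales cohere is the protocol's own stated intent, and a threshold fixed in advance is more transparent than an informal look. That is fair as a reason to report alpha. It does not supply the missing visit or fallback, nor does it reconcile SAP 4.2.1 with SAP 3.1.

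Four stronger readings are tempting, and the documents do not support them.

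- *The eligibility rule forces alpha below 0.70.* A reader might infer this from the Screening results. The direction is right, but the outcome depends on a visit that the SAP does not name and on correlations that no document gives. At 6 months, the primary time point, alpha usually passes in this model. Scores are also bounded rather than normal, and SAP 4.2.3 says that some UCLA PTSD-RI assessments yield no score.
- *Without the composite, the primary question has no planned answer.* The objective is worded as depression, anxiety and/or traumatic stress. All three scales are primary outcomes tested whatever alpha is, and multi-level models are planned for every primary outcome. What would be lost is the lead test.
- *Only the composite is powered.* Protocol 9.3.1 does name it, but Table 5 is in SD units and would serve a single scale with the same ICC and numbers.
- *The standardization constants do not exist.* The scores are collected at Screening, labelled there as baseline measures, and summarized under baseline characteristics in SAP 5.2.2. Only the visit label is wrong.

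**Conclusion.** The point stands in limited form. SAP 4.2.1 makes the composite conditional on alpha of at least 0.70, with no visit and no fallback, against SAP 3.1 and protocol 9.5.1. This textual conflict needs no simulation.

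The likelihood that the condition bites rests on assumed correlations, cutoff prevalences, tracking over time and normality. If alpha is taken at Screening, failure is probable unless the scales correlate at about 0.8 or more among screened youth. If it is taken at 6 months, failure is unlikely unless they correlate at about 0.5, or at about 0.6 with strong tracking of scores over time. The consequence of failure is the loss of a single lead test, leaving three unadjusted tests.

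The Pre-Entry label is a separate and smaller error in the same paragraph.

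**What to change.** In SAP 4.2.1, delete the words *If coherent* and the threshold attached to them. State that the three-scale composite is always created and tested as the lead primary analysis, with the three single scales analysed as already planned. Report Cronbach's alpha at Screening and at 6 months as description only.

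For PHQ-9, GAD-7 and UCLA PTSD-RI, replace the Pre-Entry reference with Screening in the standardization rule and in SAP 4.1.2.

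Naming a visit for alpha and a prespecified fallback with multiplicity control would also close the gap, but it would keep a condition that the protocol does not have.

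The cost is a few sentences of SAP wording; the design figures do not change. The change should be made before outcomes are seen by arm. SAP 4.1 already requires modifications to outcome measures made after the team has seen post-entry data to be identified in the report. The downside is that a composite with modest alpha may be reported and must then be read alongside its components.

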Eligibility screening will be initiated after informed consent and assent (if applicable) are provided. As part of the youth informed consent/assent process, youth will be asked whether they are willing to identify a caregiver and provide written permission for the caregiver to participate in the study. Youth who cannot identify a caregiver or do not otherwise provide written permission for caregiver participation remain eligible to enroll as youth can benefit from participation in the intervention without caregivers. If the identified caregiver agrees to participate, they will be introduced to the study and asked to provide informed consent for their own participation. This can be done at any point between youth screening and the first caregiver group session.

Given that each TI-CBT and Discussion Control group should include 6-10 youth per group, sites will need to identify a pool of 12-20 eligible youth to be enrolled/randomized at one time (refer to [Section 6.3.3](#)). Enrollment/randomization must occur within 60 days of each youth participant initiating the screening process. Therefore, sites must screen a sufficient number of potential youth participants within this time period to ensure that 12-20 can be enrolled/randomized on a given

day. The first TI-CBT Intervention and Discussion Control group sessions will be conducted on the day of enrollment/randomization.

Groups will be mixed gender unless a site determines that single gender groups are more appropriate for youth participants during the ADAPT-ITT process. Sites will develop appropriate SOPs accounting for the gender composition and related recruitment process as determined appropriate from the ADAPT-ITT process.

Once a sufficient pool of eligible youth has been identified, the site will schedule the Entry Visit and first group session (the first group session will occur on the day of the Entry Visit). Prior to the Entry Visit, eligible youth will be scheduled for a Pre-Entry Visit to complete baseline evaluations. This visit can occur on the same day or within 14 days prior to the Entry Visit. Youth who are screened more than 60 days prior to enrollment must be re-screened for all inclusion and exclusion criteria prior to enrollment. The youth will not be enrolled if deemed ineligible following repeat of screening evaluations. For details on randomization, refer to [Sections 6.3.3](#) and [9.3](#).

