### 5.7.2 Risk of Contamination for the TI-CBT and Control Arm

There is unavoidable risk of contamination in this study but multiple steps to minimize contamination will be taken. Youth and caregivers in both the TI-CBT and Discussion Control groups may be recruited from the same HIV clinics, and it is possible that they will discuss their experiences in the study. However, the TI-CBT and Discussion Control groups will occur at different times to minimize the risk of contact between members of study arms. IYL and adult study staff leading the TI-CBT Arm group sessions will not have study related contact with the IYL and adult study staff leading the Discussion Control groups.

An electronic questionnaire assessing contamination will be administered at the 6-month Follow-up Study Visit to youth and caregiver in both the TI-CBT and Discussion Control groups. Youth and caregivers will be asked about any discussion of concepts or tools they learned in their assigned group with study participants randomized to the other group. Youth and caregivers will be asked to indicate specific topics discussed with participants in the other group.

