Group treatment results in correlated responses due to participant interactions with a shared group of facilitators and participants. Failure to account for this correlation can increase false positive (type I error) rates. Furthermore, each site may feature up to two waves (Figure 1). Within each wave, one group of participants receives experimental TI-CBT while the other receives Discussion Control. Waves are subsequent, rather than concurrent, and group leaders are common between waves and within site. Thus, wave may reflect temporality, e.g., treatment effects may change as leader experience increases, as well as between-group differences due to changes in group composition. Between-site heterogeneity is also expected. Multi-level models are commonly used to account for correlation within effect estimation, and also permit adjustment for wave and site, as well as additional covariates which can increase efficiency.

[figure not shown]

Figure 1. Structure of study site featuring two waves.

Supplementary analyses will be conducted separately for all primary outcome measures within the ITT analysis population using a multi-level model with two levels: individuals (level-1) nested within groups (level-2). Wave and site will be treated as fixed effects (i.e., adjusted for as covariates), along with other characteristics, as adjustment for strong prognostic factors can increase efficiency. Small-sample adjustment will be performed to ensure that inference is valid at the 5% significance level.

Potential covariates may include gender, number of sessions attended, caregiver participation, living situation (with or without parents), route of infection, and reported contamination between groups. Variable selection techniques will be used to identify candidate predictors strongly associated with each outcome among the ITT analysis population. Variables with $p < 0.20$ within single variable models will be considered candidates for the final adjusted model. Candidate predictors will be selected into the final model following discussion with the protocol team to confirm clinical relevance (or prior evidence) and exclude (or combine) one or more covariates if highly correlated or colinear.

The GAD-7 and PHQ-9 assessments are scorable for all youth, unlike the UCLA PTSD-RI (see Section 4.2.3). If more than 10% of UCLA PTSD-RI assessments are unscorable at the PCD, another supplementary analysis will repeat the primary analysis for an additional composite

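### The supplementary multi-level model may adjust for variables that arise after randomization (sessions attended, reported contamination, possibly caregiver participation), so its treatment effect may no longer be the intention-to-treat effect

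*SAP*

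**What the plan says.** SAP 4.2.1 (Supplementary Analyses) fits a two-level model, youth within groups, to each primary outcome in the ITT population, with wave and site as fixed effects. It justifies further adjustment by the efficiency gained from strong prognostic factors. The list begins: "Potential covariates may include gender, number of sessions attended, caregiver participation". It continues with living situation, route of infection and reported contamination.

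Selection has two steps. First: "Variables with $p < 0.20$ within single variable models will be considered candidates for the final adjusted model". The protocol team then discusses the candidates, looking at clinical relevance or prior evidence and at collinearity.

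Protocol 9.5.1 has a similar list: "Potential covariates include gender, caregiver participation, route of infection, and reported contamination between groups". It mentions number of visits only as a group characteristic; the SAP adds sessions attended to the list of potential covariates.

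On timing:
- **Sessions attended.** SAP 4.1.2 puts enrollment, randomization and Group Session 1 on Day 0. Protocol Table 4 also counts sessions attended as a TI-CBT acceptability outcome.
- **Contamination.** Protocol 5.7.2: "An electronic questionnaire assessing contamination will be administered at the 6-month Follow-up Study Visit".
- **Caregiver participation.** Youth permission is sought at consent and documented at the Screening Visit (Protocol 4.6, 6.3.1). Of the caregiver's own consent, Protocol 4.6 says: "This can be done at any point between youth screening and the first caregiver group session". Caregiver enrollment follows youth enrollment. The SAP does not say which of these it means.

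**The concern.** A covariate measured before randomization cannot be changed by the arm, so adjusting for it leaves the target of estimation alone. A covariate that arises afterwards can be changed by the arm. Adjusting for it then removes any part of the effect that runs through it. It also induces an association between arm and any unmeasured trait, such as motivation, that drives both the covariate and the outcome.

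Contamination has a further problem. Only TI-CBT has a manual; Discussion Control facilitators have no set agenda (Protocol 5.1.2). Reported sharing of content therefore cannot mean the same thing in both arms.

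At stake is the only covariate-adjusted efficacy estimate described in SAP 4.2. It is run for every primary outcome and its final models go into the primary analysis report (SAP 5.2.6). If it disagreed with the t-test, a reader could not tell over-adjustment from a fragile result. SAP 4.2.1 itself rests freedom from bias on randomization.

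**Working it through.** **1. The plan's own yardstick.** The only stated figure nearby is the detectable difference of 0.42-0.62 SD (SAP 2.4). With m groups per arm of n youth, SE = √[2(1+(n−1)ICC)/(mn)], and power comes from a noncentral t with 2(m−1) df.
- m=16, n=8, ICC=0.05: SE = √(2×1.35/128) = 0.145, detectable 0.421.
- m=12, n=8, ICC=0.15: SE = √(2×2.05/96) = 0.207, detectable 0.606. Table 5 shows 0.61 and the text 0.62.

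All 36 cells of Table 5 reproduce within rounding, so 0.42 SD is a sound yardstick.

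**2. Formula for the shift.** Lower scores are better. Let arm raise attendance by a SD. Let attendance act on the outcome with slope b. Let an unmeasured trait act on the outcome with slope c and correlate ρ with attendance. Then

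adjusted effect = total effect − a(b + cρ).

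If a = 0, nothing shifts. None of a, b, c, ρ is in the documents. The ranges assumed were a = 0, 0.25, 0.5; b = 0, −0.2, −0.4; c = −0.4; ρ = 0 or 0.4.

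Worst corner (a=0.5, b=−0.4, ρ=0.4): a(b+cρ) = 0.5×(−0.4−0.16) = −0.28. A total effect of −0.50 becomes −0.22, and a total effect of 0 becomes +0.28. Of the 0.28, 0.20 is the path through attendance and 0.08 comes from the unmeasured trait.

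**3. Simulation with clustering** (800 trials per setting, 14 groups per arm of 8, ICC 0.10, site-wave pair effects, t with 13 df):

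| Setting | Without attendance | With attendance |
|---|---|---|
| True −0.50, a=0 | −0.49 to −0.51 | −0.49 to −0.51 |
| True −0.50, a=0.25 | −0.49 to −0.51 | −0.35 to −0.50 |
| True −0.50, a=0.5 | −0.49 to −0.51 | −0.22 to −0.49 |
| Power, worst corner | 79% | 28% |
| True 0, worst corner: estimate | +0.01 | +0.28 |
| True 0, worst corner: rejection | 3% | 43% |

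Without attendance, null rejection stayed at 2.0-4.6% throughout.

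**4. Does the p<0.20 screen filter these variables out?** No. Attendance passed in 86-100% of trials whenever it was related to outcome. With a = 0, the screen by itself did no harm: null rejection was 3.0-6.2%.

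**5. Sensitivity to the attendance level** (3,000 trials, 128 per arm, no clustering, no true effect). Sessions = μ + shift×arm + U + e, limited to 0-6; outcome = −0.5U + N(0, 0.8²); U and e standard normal. The outcome SD is √(0.25+0.64) = 0.94.
- μ=4: the share of controls attending at least five sessions is P(N(0,2) ≥ 1) = 24%. Shifts of 0.5 and 1 session give +0.12 and +0.24 raw, or 0.13 and about 0.25 SD. Nominal 5% tests reject in 19% and 53% of trials.
- The predecessor study in Rwanda had 95% attending at least five of six sessions (Protocol 1.2.1). Matching that needs μ = 5 + 1.645×√2 = 7.33. The same shifts give +0.04 and +0.06 raw, about 0.04-0.07 SD, because the cap leaves little room for the arms to differ.
- Shift 0: no bias at either level.

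**6. Against the yardstick.** 0.04-0.07 SD is 10-17% of 0.42 (6-11% of 0.62). 0.13-0.28 SD is 31-67% of 0.42 (21-45% of 0.62).

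These calculations cover attendance only. The documents give nothing from which to size the effect of adjusting for contamination.

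**The case against.** The strongest reply is that little depends on this model. The primary analysis is an unadjusted group-level paired t-test, and the MITT and imputation supplements repeat that test rather than this model. The covariates are only potential ones, and the team reviews them. Both arms have the same number and timing of sessions (Protocol 5.1.2), with matched transport, compensation and refreshments, so attendance may not differ by arm. In that case adjustment does no harm and can add power: from 77% to 90% in the most favourable simulated setting.

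Most of this stands and limits the point. It does not remove it. The team review addresses relevance and collinearity, not timing. Equal planned dose does not guarantee equal attendance, and whether arm shifts attendance is unknown when the SAP is fixed. Running the model in the ITT population does not help either: including every youth does not restore the protection of randomization once the model conditions on a consequence of allocation.

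Four stronger readings are tempting, and the documents do not support them.
- A reader might infer that the adjusted estimate is certainly biased. That requires arm to affect the covariate, which is plausible for contamination but not shown for attendance.
- A reader might infer that adjustment could erase or reverse a real effect. In the settings run, effects of the size the trial is powered for were attenuated only. In step 5 with μ=4, a true −0.42 SD (−0.40 raw) becomes −0.40+0.12 = −0.28 or −0.40+0.24 = −0.16 raw.
- A reader might infer that the p<0.20 screen alone breaks the 5% level. Step 4 does not show that.
- A reader might infer that caregiver participation must go entirely. Youth permission recorded at screening is a legitimate baseline covariate.

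**Conclusion.** The point holds for the supplementary model only. Sessions attended and reported contamination are post-randomization, and caregiver participation is too if it means enrollment or attendance. The selection rule tends to keep such variables and leaves the final model open until outcomes have been modelled. If arm affects any of them, the adjusted coefficient is not the ITT effect and can be biased.

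For attendance the size runs from nil, through about 0.04-0.07 SD at the predecessor's attendance level, to 0.13-0.28 SD under less favourable assumptions. Every non-zero figure rests on assumed parameters and is illustrative. No primary or secondary conclusion depends on it. It should still be corrected before the analysis, because the estimate will be reported beside the primary result and the remedy is cheap.

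**What to change.** In SAP 4.2.1:
- Name the covariates in advance and use only those measured before randomization: site, wave, gender (the randomization stratum), route of infection, living situation, the screening score of the outcome being analysed, and youth permission for caregiver participation as recorded at screening.
- State how youth with an unscorable screening UCLA PTSD-RI stay in the model, for example with an unscorable indicator and a fixed value in place of the score. Youth can qualify on PHQ-9 or GAD-7 alone (Protocol 4.1.6), so without such a rule some would drop out.
- Delete the p<0.20 selection and the later choice of covariates.
- Move sessions attended and reported contamination to separate analyses labelled exploratory, and do not present them as checks on the ITT result.

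Align Protocol 9.5.1, including its mention of number of visits as a group characteristic.

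The cost is wording plus the handling of unscorable screening scores. No new data are needed. The plan gives up any precision that attendance might have added, but it could not have known beforehand that this gain was free of bias.
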